6.1. Inclusion Criteria

Patients are eligible to be included in the study only if they meet all of the following criteria at screening:

Type of Patient and Disease Characteristics

- [1] Have completed the final treatment study visit of an originating study, such as Study JAHZ or Study JAIA.

Patient Characteristics

- [2] Male or nonpregnant, nonbreastfeeding female patient
 - a. Patients of child-bearing potential who are abstinent (if this is complete abstinence, as their preferred and usual lifestyle) or in a same-sex relationship (as part of their preferred and usual lifestyle) must agree to either remain abstinent or stay in a same-sex relationship without sexual relationships with the opposite sex.
 - b. Total abstinence is defined as refraining from intercourse during the entirety of the study and for at least 1 week following the last dose of investigational product. Periodic abstinence, such as calendar, ovulation, symptothermal, post-ovulation methods, and withdrawal, are not acceptable methods of contraception.
 - c. Otherwise, patients of childbearing potential together with their partners must agree to use 2 effective methods of contraception, where at least 1 form is highly effective, for the entirety of the study and for at least 1 week following the last dose of investigational product.
 - d. The following contraception methods are considered acceptable (the patient should choose 2, and 1 must be highly effective [defined as less than 1% failure rate per year when used consistently and correctly]):
 - Highly effective birth control methods:
 - Combined (estrogen and progestogen containing) hormonal contraception associated with inhibition of ovulation: oral, intravaginal, or transdermal

- Progestogen-only containing hormonal contraception associated with inhibition of ovulation: oral, injectable, or implantable
- Intrauterine device (IUD)/intrauterine hormone-releasing system (IUS)
- Vasectomized male (with appropriate post-vasectomy documentation of the absence of sperm in the ejaculate).
- Effective birth control methods:
 - Male or female condom with spermicide. It should be noted that the use of male and female condoms as a double barrier method is not considered acceptable due to the high failure rate when these methods are combined.
 - Diaphragm with spermicide
 - Cervical sponge
 - Cervical cap with spermicide

Note: When local guidelines concerning highly effective or effective methods of birth control differ from the above, the local guidelines must be followed.

Patients of non-child-bearing potential are not required to use birth control and they are defined as:

- Women who are infertile due to surgical sterilization (hysterectomy, bilateral oophorectomy, or tubal ligation)
- Post-menopausal – defined either as
 - A woman at least 50 years of age with an intact uterus, not on hormone therapy, who has had either
 - Cessation of menses for at least 1 year
 - At least 6 months of spontaneous amenorrhea with follicle-stimulating hormone >40 mIU/mL
 - Women aged 55 years or older who are not on hormone therapy, and who have had at least 6 months of spontaneous amenorrhea
 - Women aged 55 years or older who have a diagnosis of menopause

Informed Consent

- [3] Must read and understand the informed consent approved by Eli Lilly and Company (Lilly), or its designee, and the institutional review board (IRB)/ethics review board (ERB) governing the site, and provide written informed consent.

6.2. Exclusion Criteria

Medical Conditions

- [4] Have significant uncontrolled cerebro-cardiovascular (for example, myocardial infarction, unstable angina, unstable arterial hypertension, severe heart failure, or cerebrovascular accident), respiratory, hepatic, renal, gastrointestinal, endocrine, hematologic, neuropsychiatric disorders, or abnormal laboratory values that, in the opinion of the investigator, pose an unacceptable risk to the patient if investigational product continues to be administered.
- [5] Have a known hypersensitivity to baricitinib or any component of this investigational product.
- [6] Had investigational product permanently discontinued at any time during a previous baricitinib study.
- [7] Had temporary investigational product interruption at the final study visit of a previous baricitinib study **and**, in the opinion of the investigator, this poses an unacceptable risk for the patient's participation in the study.
- [8] Have any other condition that, in the opinion of the investigator, renders the patient unable to understand the nature, scope, and possible consequences of the study or precludes the patient from following and completing the protocol.
- [9] Are currently enrolled in any other clinical study involving an investigational product or any other type of medical research, judged not to be scientifically or medically compatible with this study.

6.3. Lifestyle Restrictions

Study participants should be instructed not to donate blood or blood products during the study or for 30 days following the last dose of investigational product.

6.4. Screen Failures

Individuals who do not meet the criteria for participation in this study (screen failure) may not be rescreened.

7. Treatments

7.1. Treatments Administered

This study involves baricitinib tablets 4-mg or 2-mg administered orally QD with placebo tablets administered orally QD to maintain the blind. [Table JAIM.3](#) shows the treatment regimens.

Table JAIM.3. Treatment Regimens

Treatment Group	Treatments Administered Day 1 through Day 1092
Baricitinib 4-mg QD ^a	1 baricitinib 4-mg tablet and 1 placebo tablet matching baricitinib 2-mg
Baricitinib 2-mg QD	1 baricitinib 2-mg tablet and 1 placebo tablet matching baricitinib 4-mg

Abbreviations: eGFR = estimated glomerular filtration rate; QD=once daily.

^a Patients randomized to placebo during the originating study with eGFR <60 mL/min/1.73 m² (based on the last eGFR assessment prior to entry into Study JAIM) who are randomized to the 4-mg dose will receive a dose of 2-mg QD. Patients randomized to active treatment during the originator study who were receiving an adjusted dose due to renal impairment will continue on the same adjusted dose in Study JAIM.

Note: Patients randomized to placebo during the originating study will be randomized 1:1 to blinded baricitinib 2-mg or baricitinib 4-mg. Dose adjustment for patients newly randomized to baricitinib, if necessary, will be based on the last available estimated glomerular filtration rate (eGFR) from the originating study.

The investigator or his/her designee is responsible for the following:

- Explaining the correct use of the investigational agent(s) to the patient
- Verifying that instructions are followed properly
- Maintaining accurate records of investigational product dispensing and collection
- At the end of the study returning all unused medication to Lilly, or its designee, unless the sponsor and sites have agreed that all unused medication is to be destroyed by the site, as allowed by local law.

7.1.1. Packaging and Labelling

Lilly (or designee) will provide the following primary study materials:

- Tablets containing 4-mg of baricitinib
- Tablets containing 2-mg of baricitinib
- Tablets containing placebo to match 4-mg baricitinib
- Tablets containing placebo to match 2-mg baricitinib

Investigational product will be dispensed to the patient at the principal investigator's study site. Investigational product packaging will contain enough tablets for the longest possible interval between visits.

Investigational product will be labeled according to the country's regulatory requirements.

Patients will be instructed to take 2 tablets, 1 tablet from 2 different bottles, each day.

All investigational products will be stored, inventoried, reconciled, and destroyed according to applicable regulations. Investigational products will be supplied by Lilly or its representative in accordance with current Good Manufacturing Practices and will be supplied with lot numbers, expiry dates, and certificates of analysis (as applicable).

7.2. Method of Treatment Assignment

Patients who meet all criteria for enrollment will be assigned to baricitinib treatment (2-mg QD or 4-mg QD) according to the treatment they were receiving in the originating study. Patients randomized to active treatment during the originating study will be assigned to the same, blinded dose of baricitinib in Study JAIM. Patients randomized to placebo during the originating study will be randomized 1:1 to blinded baricitinib treatment (2-mg QD or 4-mg QD). Randomization will be stratified by corticosteroid dose on the day of randomization (<10 mg/day; ≥10 mg/day prednisone or equivalent), and region (defined in the SAP). Patients with renal impairment (as defined in Section 7.2.2) who are randomized to baricitinib 4-mg QD will receive baricitinib 2-mg QD.

Assignment to treatment groups will be determined using an interactive web-response system (IWRS). The IWRS will be used to assign packages containing blinded investigational product to each patient. Site personnel will confirm that they have located the correct packages by entering a confirmation number found on the packages into the IWRS before dispensing to the patient.

7.2.1. Selection and Timing of Doses

Investigational product will be provided to patients at Visit 1.

Two tablets should be taken orally each day, without regard to food and, if possible, at approximately the same time every day.

7.2.2. Dose Adjustment for Renal Impairment

The dose adjustment for renal impairment will be managed by IWRS to ensure maintenance of the treatment blind. For patients randomized to active treatment during the originating studies, the eGFR value from the originating screening visit will be used by IWRS to assign the treatment doses accordingly. For patients randomized to placebo in the originating studies, the last available eGFR value from the originating study will be used by IWRS to assign the treatment doses accordingly.

- Patients with documented renal impairment (defined as eGFR ≥40 to <60 mL/min/1.73 m²), who are assigned to active treatment (either to the baricitinib 4-mg arm or the baricitinib 2-mg arm) will receive a baricitinib 2-mg QD dose by the IWRS.
- No dose adjustment will be made for patients with eGFR ≥60 mL/min/1.73 m².

The rationale of dose adjustment for patients with documented renal impairment is detailed in Section 5.4.

Interruption criteria due to eGFR during the treatment period is discussed in Section 8.1.1.

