Abbreviations: ANA = antinuclear antibody; BILAG = British Isles Lupus Assessment Group; BP = blood pressure; CLASI = Cutaneous Lupus Erythematosus Disease Area and Severity Index; C-SSRS = Columbia-Suicide Severity Rating Scale; dRVVT = Dilute Russell's Viper Venom Time; dsDNA = double-stranded deoxyribonucleic acid; EQ-5D-5L = 5-level EuroQol-5 Dimensions; ET = early termination; FACIT = Functional Assessment of Chronic Illness Therapy; HBcAb = hepatitis B core antibody; HBsAb = hepatitis B surface antibody; HBV DNA = hepatitis B virus deoxyribonucleic acid; Ig = immunoglobulin; IWRS = interactive web-response system; NRS = numerical rating scale; PGI-S = Patient's Global Impression of Severity; RNP = ribonucleoprotein; QIDS-SR16 = 16-Item Quick Inventory of Depressive Symptomatology-Self Report; SF-36v2 = Short-Form 36-item Health Survey version 2; SLE = systemic lupus erythematosus; SLEDAI-2K = Systemic Lupus Erythematosus Disease Activity Index 2000; SLICC/ACR = Systemic Lupus Erythematosus International Collaborating Clinics/American College of Rheumatology; SSA/Ro = Sjögren's-Syndrome-related antigen A; SSB/La = Sjögren syndrome type B antigen/Lupus La protein; V = visit; W = week; WPAI = Work Productivity and Activity Impairment.

- ^a Patients who discontinue from investigational product (IP) early should complete the ET visit and proceed to post-treatment follow-up.
- ^b All patients should return for Visit 801, a post-treatment follow-up visit, 28±5 days after the last dose of IP. Patients who discontinue IP but remain in the study for at least 28±5 days without IP, can combine their Visit 11/ET with their Visit 801 (post-treatment follow-up visit).
- ^c Visit 1 of Study JAIM should occur on the same day as the final visit of the originating study. Assessments/procedures required for both Visit 1 of Study JAIM and the final visit of the origination study should only be performed once.
- ^d At each time point, 3 replicate readings should be made at approximately 30- to 60-second intervals. Blood pressure is recorded as the average of these 3 readings. A single pulse measurement should be made simultaneously with at least 1 of the readings at each time point (Section 9.4.1. for details on vital signs).
- ^e Adverse events that are ongoing at the completion of the originating trial should be reported as pre-existing conditions at Visit 1 for Study JAIM.

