- ^o Clinical chemistry will include the following value calculated from serum creatinine: eGFR (calculated using the Modification of Diet in Renal Disease [MDRD] isotope dilution mass spectrometry traceable method).
- ^p Patients should not eat or drink anything, except water, for 12 hours prior to sample collection. If a patient attends these visits in a nonfasting state, the sample should still be collected. This will not be considered a protocol violation.

3. Introduction

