8.1. Discontinuation from Study Treatment

8.1.1. Temporary Interruption of Investigational Product

In some circumstances, it may be necessary to temporarily interrupt treatment as a result of AEs or abnormal laboratory values that may have an unclear relationship to investigational product. It is recommended that the investigator consult with Lilly (or its designee) before temporarily interrupting therapy for reasons other than those defined in [Table JAIM.4](#). Retest timing and frequency is at the investigator's discretion.

Investigational product that was temporarily interrupted because of an AE or abnormal laboratory value, not specifically covered in [Table JAIM.4](#), may be restarted at the discretion of the investigator. Investigational product must be held in the following situations and may only be resumed as noted in the table.

Table JAIM.4. Criteria for Temporary Interruption of Investigational Product

Hold Investigational Product if the Following Abnormalities Occur:	Investigational Product May be Resumed When:
WBC count <2000 cells/ μ L ($<2.00 \times 10^3/\mu$ L or <2.00 GI/L)	WBC count ≥ 2500 cells/ μ L ($\geq 2.50 \times 10^3/\mu$ L or ≥ 2.50 GI/L)
ANC <1000 cells/ μ L ($<1.00 \times 10^3/\mu$ L or <1.00 GI/L)	ANC ≥ 1200 cells/ μ L ($\geq 1.2 \times 10^3/\mu$ L or ≥ 1.2 GI/L)
Lymphocyte count <300 cells/ μ L ($<0.30 \times 10^3/\mu$ L or <0.30 GI/L)	Lymphocyte count ≥ 500 cells/ μ L ($\geq 0.50 \times 10^3/\mu$ L or ≥ 0.50 GI/L)
Platelet count <25,000/ μ L ($<25 \times 10^3/\mu$ L or <25 GI/L)	Platelet count $\geq 50,000/\mu$ L ($\geq 50 \times 10^3/\mu$ L or ≥ 50 GI/L)
eGFR <40 mL/min/1.73 m ² for patients with eGFR ≥ 60 mL/min/1.73 m ²	eGFR ≥ 50 mL/min/1.73 m ²
ALT or AST >5 x ULN	ALT and AST return to <2 x ULN and possible DILI has been ruled out, and IP is not considered to be the cause of enzyme elevation
Hemoglobin <8 g/dL (<80.0 g/L)	Hemoglobin ≥ 9 g/dL (≥ 90.0 g/L)
Symptomatic herpes zoster	All skin lesions have crusted and are resolving
Infection that, in the opinion of the investigator, merits the IP being withheld ^a	Resolution of infection that, in the opinion of the investigator, merits the IP being restarted

Abbreviations: ALT = alanine aminotransferase; ANC = absolute neutrophil count; AST = aspartate aminotransferase; eGFR = estimated glomerular filtration rate; IP = investigational product; ULN = upper limit of normal; WBC = white blood cell.

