9.2. Adverse Events

Investigators are responsible for monitoring the safety of patients who have entered this study and for alerting Lilly or its designee of any event that seems unusual, even if this event may be considered an unanticipated benefit to the patient.

The investigator is responsible for the appropriate medical care of patients during the study.

Investigators must document their review of each laboratory safety report.

The investigator remains responsible for following, through an appropriate health care option, AEs that are serious or otherwise medically important, considered related to the investigational product or the study, or that caused the patient to discontinue the investigational product before completing the study. The patient should be followed until the event resolves or stabilizes with appropriate diagnostic evaluation. The frequency of follow-up evaluations of the AE is left to the discretion of the investigator.

Lack of drug effect is not an AE in clinical studies, because the purpose of the clinical study is to establish treatment effect.

After the informed consent form (ICF) is signed, study site personnel will record via eCRF the occurrence and nature of each patient's preexisting conditions, except SLE, as it is the disease under treatment in the study. In addition, site personnel will record any change in the condition(s) and any new conditions as AEs. Investigators should record the following via eCRF for each AE: start date, stop date (if applicable), severity, and their assessment of the potential relatedness of each AE to protocol procedure or investigational product, via eCRF.

The investigator will interpret and document whether or not an AE has a reasonable possibility of being related to study treatment, study device, or a study procedure, taking into account the disease, concomitant treatment or pathologies.

A "reasonable possibility" means that there is a cause and effect relationship between the investigational product, study device and/or study procedure and the AE.

The investigator answers yes/no when making this assessment.

Planned surgeries and nonsurgical interventions should not be reported as AEs, unless the underlying medical condition has worsened during the course of the study.

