Section 8.1.1 - Temporary Interruption of Investigational Product; Table JAIM.4 . Criteria for Temporary Interruption of Investigational Product	Delete interruption criterion based on eGFR <30.	Because of study blinding, “baseline” eGFR will not be known to investigators (For patients assigned to baricitinib in originating study, eGFR from baseline in the originating study is used. For patients assigned to placebo in originating study, eGFR from baseline in JAIM is used). The more conservative criteria (eGFR <40) will be used.
Section 9.4.6 - Hepatitis B Virus (HBV) DNA Monitoring	Text was modified to describe HBV monitoring every 6 months after W60.	Text was added to account for the increased interval of HBV testing after Week 60 due to the removal of study visits V8, V10, V12, and V14.
Section 10.3.1 – General Statistical Considerations	Text was updated to include efficacy and specify that integrated data will be assessed.	Updated to clarify that the safety and efficacy data would be (in addition to) assessed in the context of integrated data
Section 10.3.3 – Efficacy Analyses	Wording was updated to include the ANCOVA model.	ANCOVA model was needed to analyze SLICC/ACR responses.
Section 10.3.3.1 – Missing Data Imputation	Last Observation Carried Forward was changed to Modified Last Observation Carried Forward.	Text was changed to specify the methodology used in which to impute missing data.
Section 10.3.4 – Safety Analyses	Text added specifying how the endpoints of safety and tolerability would be analyzed and to outline safety measures to be reported specifically for JAIM.	To specify that the primary endpoints would be analyzed as a part of the integrated safety analyses for SLE and as such, will be reflected in the integrated safety analysis plan for SLE and to outline the categorical safety measures to be reported specifically for JAIM.
Section 10.3.4.1 – Adverse Events	PSAP analysis was removed	PSAP and iSAP are redundant terminology.
Section 10.3.4.3 - Vital Signs, Physical Findings, and Other Safety Evaluation	Text specifying that further analysis will be planned in the SAP iSAP was removed	Upon review of the section, the text was deemed unnecessary and was removed.

Revised Protocol Sections

Note: Deletions have been identified by striketroughs. Additions have been identified by the use of underscore.

1. Synopsis

Objectives and Endpoints

- | | |
|---|--|

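### Protocol 7.2.2 and SAP 5.4 limit the renal step-down to eGFR 40 to below 60, so read literally a 4-mg patient below 40 is outside a rule that other sections apply to every eGFR below 60

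*Protocol*

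**What the plan says.** Two versions of the same dosing trigger stand in the plan.

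**With a lower bound of 40.** Protocol 7.2.2 describes what the IWRS does. It gives 2 mg to "Patients with documented renal impairment (defined as eGFR ≥40 to <60 mL/min/1.73 m²), who are assigned to active treatment", and makes no adjustment at eGFR 60 or above. SAP 5.4 repeats both bullets. Protocol 7.2 does not define renal impairment itself but points to 7.2.2: "Patients with renal impairment (as defined in Section 7.2.2) who are randomized to baricitinib 4-mg QD will receive baricitinib 2-mg QD". SAP 5.3 uses the same cross-reference. Protocol 7.4 says that dose adjustment strictly follows 7.2.1 and 7.2.2.

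**Without a lower bound.** Table JAIM.3 footnote a (Protocol 7.1) steps down "Patients randomized to placebo during the originating study with eGFR <60 mL/min/1.73 m²" who are randomized to 4 mg. Protocol 5.1 defines renal impairment in former placebo patients as eGFR below 60 and gives them 2 mg. Protocol 5.4 and SAP 6.2 also step down 4-mg patients with eGFR below 60.

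For former placebo patients the IWRS uses the last available eGFR from the originating study. For patients already on active drug it uses the originating screening value. JAIM sets no numeric eGFR limit for entry; exclusion [4] leaves renal disorders and abnormal laboratory values to the investigator's opinion.

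**The concern.** The lower bound appears only in the section that instructs the dosing system and in its SAP copy. A patient with eGFR below 40 meets neither bullet of 7.2.2. Because 7.2 steps down only patients who have renal impairment as 7.2.2 defines it, a literal reader would not step down a 4-mg patient below 40.

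This runs against the purpose of the rule. Protocol 5.4 explains that baricitinib exposure rises as renal function falls, and that 2 mg keeps exposure in impaired patients within that of 4 mg at eGFR 60 or above. The patients left without a rule are those with the lowest renal function. What is at stake is the starting dose of a few patients, if the IWRS was programmed from 7.2.2 alone.

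**Working it through.** The plan gives no figure to reproduce. The check sets the rules side by side for a former placebo patient randomized to 4 mg and then bounds the number of patients.

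**Step 1: the rules by eGFR band**

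| Last eGFR (mL/min/1.73 m²) | Protocol 7.2.2 and SAP 5.4 (adopted by Protocol 7.2 and SAP 5.3) | Protocol 5.1, 5.4, Table JAIM.3 footnote a, SAP 6.2 |
|---|---|---|
| 60 or above | no adjustment | no adjustment |
| 40 to below 60 | 2 mg | 2 mg |
| below 40 | no rule; outside the definition | 2 mg |

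The two sets differ only in the last row.

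**Step 2: can the last row occur?** No JAIM entry criterion sets an eGFR floor. The deciding value for former placebo patients is the last one from the originating study, so a floor at that study's screening, if there was one, would not guarantee 40 or more at the end of it. The originating protocols' eGFR limits are not in the documents. Patients already on active drug are dosed from their originating screening value, and Table JAIM.3 keeps any adjusted dose they were on, so the gap mainly concerns former placebo patients.

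**Step 3: how many patients?**

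Inputs from the documents: planned enrolment 1100 (Protocol 5.2 and 10.1); former placebo patients randomized 1:1 (Protocol 7.2). Assumed, because the documents do not give them: the share of JAIM patients who come from placebo (one quarter, one third or one half), and the proportion of these with a last eGFR below 40 (0% to 2%).

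Former placebo patients randomized to 4 mg = 1100 × placebo share ÷ 2. Patients in the gap = that number × proportion below 40.

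| Placebo share | Randomized to 4 mg | At 0% | At 0.5% | At 1% | At 2% |
|---|---|---|---|---|---|
| 1/4 | 1100 × 1/4 ÷ 2 = 137.5 | 0 | 0.7 | 1.4 | 2.8 |
| 1/3 | 1100 × 1/3 ÷ 2 = 183.3 | 0 | 0.9 | 1.8 | 3.7 |
| 1/2 | 1100 × 1/2 ÷ 2 = 275 | 0 | 1.4 | 2.8 | 5.5 |

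The gap therefore covers 0 to about 4 patients at a one-third share, and 0 to about 6 over the whole range.

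**The case against.** The strongest reply is that the answer is already in the documents. For exactly this patient, Table JAIM.3 footnote a and Protocol 5.1 give 2 mg, SAP 6.2 agrees, and 7.2.2 itself refers to 5.4, which also uses eGFR below 60. On this view 7.2.2 is merely silent and the other sections fill the gap. Harm would need both an IWRS built from 7.2.2 alone and patients below 40, and the documents show neither. There are safeguards too: eGFR is part of the chemistry panel at Visit 1, exclusion [4] lets the investigator keep a patient out, and "Investigators must document their review of each laboratory safety report".

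Much of this stands, and it is why the point is minor. It does not remove the inconsistency: 7.2.2 is where the IWRS action is specified, 7.2 relies on its definition, and 7.4 tells the reader to follow it strictly. The safeguards are also partial. Site staff are blinded to dose, so they can withhold product but cannot see whether a 4-mg patient was stepped down.

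Three stronger readings are tempting, and the documents do not support them.

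- A reader might infer that the plan orders 4 mg below 40. No passage does so; one set of sections has no rule and the other gives 2 mg.
- A reader might infer that Table JAIM.4 adds a third, conflicting instruction of no product below 40. That row is an on-treatment interruption rule, not an assignment rule, and is written "for patients with eGFR ≥ 60 mL/min/1.73". Extending it to patients who enter below 40 would rest only on the rationale in the amendment summary ("The more conservative criteria (eGFR <40) will be used"), which explains a deletion and does not alter the row's scope.
- A reader might infer that former placebo patients below 40 should not start product. That would contradict Protocol 5.1 and Table JAIM.3, which give them 2 mg. It would not match the resumption threshold of 50 in Table JAIM.4. Applied to former placebo patients only, it could also hint at the originating-study assignment that 7.2.2 and 7.3 protect.

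**Conclusion.** The concern holds as a wrong threshold in the controlling dosing section. Read literally, 7.2 with 7.2.2 puts a 4-mg patient below 40 outside the step-down, against four other places in the plan. Severity is minor. The estimate of 0 to about 6 patients rests on an assumed placebo share and an assumed prevalence, and it includes zero. An effect on anyone's dose further requires an IWRS programmed from 7.2.2 alone, which cannot be judged without its specification. No length of exposure at the wrong dose is claimed. No harm to the analysis is claimed either: SAP 6.2 already keeps stepped-down patients in the 4-mg arm and lists randomized against received treatment for patients with eGFR below 60.

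**What to change.** In Protocol 7.2.2 and SAP 5.4, replace the range of 40 to below 60 with eGFR below 60 mL/min/1.73 m². Protocol 7.2 and SAP 5.3 then follow by cross-reference, and all sections agree. Check the IWRS specification against the corrected rule. If patients have already been assigned, the existing SAP 6.2 listing shows whether anyone below 40 who was randomized to 4 mg received it.

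The cost is one definition changed in two places and one specification check. No new procedure, visit, analysis or entry restriction is needed.
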